5.2 Schedule of Events

	Pre-Operative	Procedure	Post Op Day: 7	Post Op Day: 14	Post Op Day: 30	Post Op Day: 90	Post Op Month: 6	Post Op Month: 12
Informed Consent	X							
Inclusion/Exclusion Criteria	X							
Demographics & Medical History	X							
Vascular Access History	X							
Physical Exam	X		X	X	X	X	X	X
Blood Draw	X		X	X	X	X		
Device Placement		X						
Palpable Thrill and / or Bruit		X	X	X	X	X	X	X
[REDACTED]		X			X	X	X	X
Revisions to Circuit			X	X	X	X	X	X
Adverse Events		X	X	X	X	X	X	X

5.3 Informed Consent Process

All patients must provide informed consent prior to any study-related procedures being performed. The case history (*i.e.*, source documents / Subject chart) for each Subject shall document such informed consent was obtained. The Institutional Review Board (IRB) approved consent form (ICF) will be signed and personally dated by the Subject or his / her legally authorized representative, and the Investigator / designee who conducted the informed consent discussion.

Subjects enrolled under the original protocol (3-DEC-2013) should not be re-consented under Amendment 2 [REDACTED] if:

- the vascular graft has been abandoned prior to the Day 90 follow-up visit
- the vascular graft has been explanted

CONFIDENTIAL INFORMATION

[REDACTED] Protocol Template

Revision#: 1

Doc Type: GC

[REDACTED]

[REDACTED]

[REDACTED]

The original signed ICF(s) will be retained in the Subject records. A copy of the signed informed consent document will be given to the Subject for their records.

5.4 Screening

All patients who sign an informed consent form will be considered entered into the screening phase of the study. Subjects who sign an ICF are not assigned a subject ID until randomization.

The Site will keep signed informed consent forms on all screen failures and keep a record of the reason the Subject failed screening. Site will also keep any laboratory reports for those samples that were sent to [REDACTED] for processing.

If the Subject withdraws from the study prior to randomization, pre-procedure blood / serum samples need to be destroyed by either [REDACTED] or the Site. If the Site has the pre-procedure blood / serum samples, then the Site should destroy them per their institutional standards. If the pre-procedure blood / serum samples have already been shipped to [REDACTED], then [REDACTED] will be notified by Site and / or Sponsor to destroy the samples.

Case report forms (CRF) will not need to be completed for Subjects who are withdrawn from the study prior to randomization.

5.5 Enrollment

The patient is considered to be formally enrolled in the study when the randomization envelope, with the correct Subject ID number sequence, is opened before or during the Index Procedure.

If the Subject has been randomized (randomization envelope opened) and is unable to complete the index procedure, then the Subject will be discontinued from the study. CRFs will still be completed to reflect screening activities, procedure, and discontinuation. Pre-procedure blood and serum samples should be shipped to Covance for processing.

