Schedule of Events	
 Pre-procedure (within 2 days of Index Procedure) – Collection of blood and serum samples, medical history, physical exam, review of inclusion and exclusion criteria, and proper consenting prior to any study procedure or data collection Index Procedure - Implantation of vascular graft, [REDACTED], adverse events Day 7 (± 2 days) - Collection of blood and serum samples, adverse events, and revisions to the circuit Day 14 (± 2 days) – Collection of blood and serum samples, adverse events, and revisions to the circuit Day 30 (± 7 days) – Collection of blood and serum samples, [REDACTED], adverse events, and revisions to the circuit Day 90 (± 14 days) – Collection of blood and serum samples, [REDACTED], adverse events, and revisions to the circuit Month 6 (± 14 days) – Collection [REDACTED] adverse events, and revisions to the circuit Month 12 (± 14 days) – Collection of [REDACTED], adverse events, and revisions to the circuit
Central Laboratory	[REDACTED]
Core Laboratory	[REDACTED]
Contract Research Organization	[REDACTED]

CONFIDENTIAL INFORMATION

[REDACTED] Protocol Template

Revision#: 1

Doc Type: GC

List of Abbreviations

aCRF	Annotated Case Report Form
ACT	Activated Clotting Time
AE	Adverse Event
AT	Antithrombin
AV	Arteriovenous
CA	Competent Authority
[REDACTED]	[REDACTED]
CBC	Complete Blood Count
CDMS	Clinical Data Management System
CDU	Color Flow Duplex Ultrasound
CFD	Computational Fluid Dynamics
CFR	Code of Federal Regulations
CIP	Clinical Investigation Plan
cm	Centimeters
CM	Contrast Medium
COPD	Chronic Obstructive Pulmonary Disease
CRF	Case Report Form
CRO	Contract Research Organization
CT	Computed Tomography
CTA	Computed Tomographic Angiography
CVC	Central Venous Catheter
DIC	Disseminated Intravascular Coagulation
DIPA	Drug-Induced Platelet Activation Test
eCRF	Electronic Case Report Form
EIA	Enzyme Immunoassay
ePTFE	Expanded Polytetrafluoroethylene
ESRD	End Stage Renal Disease
FDA	Food and Drug Administration (United States)
Fr	French (sizing)
GCP	Good Clinical Practice
GHVG	GORE® Hybrid Vascular Graft
[REDACTED]	[REDACTED]
Hb	Hemoglobin
HCT	Hematocrit
HIPA	Heparin-Induced Platelet Activation Test
HIT	Heparin-Induced Thrombocytopenia
ICF	Informed Consent Form

CONFIDENTIAL INFORMATION

[REDACTED] Protocol Template

Revision#: 1

Doc Type: GC

iv of 36

ICH	International Conference on Harmonisation
IFU	Instructions for Use
IgA	Immunoglobulin A
IgG	Immunoglobulin G
IgM	Immunoglobulin M

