1.2.2. Nitinol Reinforced Section

The nitinol reinforced section (NRS) is comprised of ePTFE tubing, ePTFE reinforcing film, ePTFE / FEP membrane, nitinol, and an ePTFE / FEP film that bonds the nitinol section to the ePTFE reinforcing film. The NRS has a reducible diameter for loading into the constraint / delivery system and has sufficient radial force to resist migration when deployed into a blood vessel with proper over sizing.

1.2.3. Constraint / Delivery System The constraint / delivery system is comprised of an ePTFE fiber which is knitted into a tubular shape. A portion of the nitinol reinforced section is loaded into the constraint / delivery system such that the loaded section can be inserted into a blood vessel.

[REDACTED]

CONFIDENTIAL INFORMATION

[REDACTED] Protocol Template

Revision#: 1

Doc Type: GC

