4.1. Description of Population

Patients with End-Stage Renal Disease are eligible for screening for participation in the study. The Site may screen patients that are currently receiving hemodialysis through a central venous catheter (CVC), graft, or fistula and are expected to require hemodialysis through an upper arm prosthetic vascular graft.

The study has been designed with standard eligibility criteria to address any known or foreseeable factors that may compromise the outcome of the clinical investigation or the interpretation of results. Only patients who meet all of the inclusion criteria and none of the exclusion criteria will be enrolled.

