4.2. Inclusion Criteria (all responses must be YES to be eligible)

1. The patient is not a candidate for a native fistula.
2. The patient requires the creation of an upper arm vascular access graft for hemodialysis secondary to a diagnosis of End-Stage Renal Disease.

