9.4 Adverse Event Reporting and Coding

AEs will be reported on the appropriate case report form and documented in the Subject's permanent medical record.

The following information on each reported adverse event will be collected:

- Adverse Event Term
- Adverse Event Onset Date
- Relationship
- Severity
- Treatment
- Outcome
- Resolution Date

AEs will be coded using the Medical Dictionary for Regulatory Activities (MedDRA).

AE submission guidelines:

- AE reporting begins once the patient is enrolled in the study. All AEs should be reported from enrollment (study procedure) through study completion / discontinuation.
- Provide a diagnosis if possible. If unable to provide a diagnosis, report the symptoms as separate events. AEs should be reported using the full name without abbreviations or narratives.
- AEs with an outcome status of "Ongoing" should be assessed at each follow-up evaluation to determine if the event has resolved. AEs ongoing at study completion / discontinuation should be completed as "Ongoing" on the AE CRF.

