10.5. Blinding Scheme

The Subjects, as well as treating physicians, will be aware of the type of implanted graft. However, the core laboratory responsible for analyzing the blood samples will be blinded to the actual type of graft.

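### Section 5.5 lets the randomization envelope be opened before the index procedure, so non-implantation, withdrawal or a switch of graft can be decided with the arm known and may differ by arm

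*Protocol*

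**What the plan says.** Protocol 5.5 defines formal enrollment as the moment "when the randomization envelope, with the correct Subject ID number sequence, is opened before or during the Index Procedure". The same section says that a randomized subject who "is unable to complete the index procedure, then the Subject will be discontinued from the study". For such subjects it asks only for the forms covering screening, procedure and discontinuation, and for shipment of the pre-procedure samples.

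On blinding, Protocol 10.5 states: "The Subjects, as well as treating physicians, will be aware of the type of implanted graft". Only the core laboratory is blinded.

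On eligibility, Protocol 4.1 says: "Only patients who meet all of the inclusion criteria and none of the exclusion criteria will be enrolled". The Protocol Summary puts the "review of inclusion and exclusion criteria, and proper consenting prior to any study procedure or data collection" at the pre-procedure visit, within 2 days of the index procedure. The table in 5.2 marks the criteria only in the pre-operative column.

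On the devices, Protocol 1.2.5 lists nitinol sections of 6, 7, 8 and 9 mm for the test graft. Protocol 1.2.2 says this section "has sufficient radial force to resist migration when deployed into a blood vessel with proper over sizing". Protocol 8.1 names insertion of that section as one of only two added risks compared with standard grafts.

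On adverse events, Protocol 9.4 says: "All AEs should be reported from enrollment (study procedure) through study completion / discontinuation".

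**The concern.** Opening the envelope fixes the subject's place in the trial, but the graft is not yet in. If the envelope is opened before surgery, there is an interval in which the surgeon knows the allocation and can still decide not to proceed or to place a different graft. Nothing readable keeps the allocation from the subject in that interval either, and 5.9 allows withdrawal at any time.

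These decisions need not balance between arms. A vessel that does not suit the nitinol section is an obstacle to the test graft and not to a graft without one. Venous mapping before surgery follows institutional practice (Protocol 5), so no readable uniform work-up ensures that suitability for the test graft is settled before opening.

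At stake is the primary comparison, the prevalence of a positive poly-specific immunoassay at Day 7 and/or Day 14. Subjects who are never implanted have no planned result at those visits. Subjects who receive the other type of graft dilute the ITT contrast. The Protocol Summary's hypothesis is that prevalence will not differ statistically between arms (part of that sentence is redacted), so dilution pushes toward the hoped-for result.

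**Working it through.** The plan states no figure on this point, and the sample size, its inputs and the analysis of the primary endpoint are redacted. The check is therefore a comparison of sections plus a simple bound.

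**Step 1: order of events.** Eligibility review comes pre-operatively (Protocol Summary, 5.2) and before enrollment (4.1). The envelope is then opened before or during surgery (5.5), and implantation follows. Taken together, these sections limit the gap between opening and surgery to about 2 days. The gap is short, but it contains every decision about whether and what to implant.

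**Step 2: what each outcome does to the data.**

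| After opening | ITT (Protocol 10.6.2.1, SAP 5.2.1) | Day 7/14 result | As treated (Protocol 10.6.2.2, SAP 5.2.2) |
|---|---|---|---|
| Implanted as assigned | Assigned arm | Planned | Same arm |
| Not implanted, or withdraws first | Assigned arm | None planned | No implanted device to classify |
| Other type of graft implanted | Assigned arm | Can be obtained | Moves to the other arm |

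ITT is all enrolled subjects by assigned arm, so no row removes anyone from ITT. Row 2 produces missing outcomes and row 3 produces cross-over.

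**Step 3: size of the missing-outcome problem.** Let a fraction d of an arm be discontinued without a result, let p_obs be the prevalence among the rest, and let q be the unknown prevalence among those lost, with 0 ≤ q ≤ 1. Then

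p_ITT = p_obs(1 − d) + d·q,

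which runs from p_obs(1 − d) to p_obs(1 − d) + d, an interval of width d. For the between-arm difference the widths add: d_T + d_C.

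All of these rates are assumptions; the documents give none:

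- d = 2%, 5% or 10% in one arm only: width 2, 5 or 10 percentage points.
- The same fraction lost in both arms: 2 × 2 = 4, 2 × 5 = 10 or 2 × 10 = 20 points.
- 5% in the test arm and 1% in the control arm: 5 + 1 = 6 points.

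These are worst-case widths. They apply to lost subjects only, because a subject who switches graft can still supply a result.

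**Step 4: size of the cross-over problem.** Suppose fractions c_T and c_C switch, each switched subject carries the risk of the graft received, and switchers otherwise resemble the rest. Then

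Δ_ITT = [(1 − c_T)p_T + c_T·p_C] − [(1 − c_C)p_C + c_C·p_T] = (1 − c_T − c_C)(p_T − p_C).

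If the assumed 5% and 1% were all switches rather than dropouts, the factor would be 1 − 0.05 − 0.01 = 0.94, a 6% relative shrinkage of any true difference. A mixture of dropouts and switches gives less than the full effect of each kind.

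**Step 5: adverse-event start.** Protocol 9.4 first starts reporting at enrollment, then equates enrollment with the study procedure. The table in 5.2 starts collection in the procedure column. Under 5.5 enrollment can come earlier, so an event between opening and surgery is reportable on one reading and not on the other.

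**The case against.** The strongest reply is that opening the envelope shortly before surgery, after eligibility has been reviewed, is an ordinary arrangement that 5.5 deliberately allows. ITT keeps every subject in the assigned arm, and a blinded laboratory reads the primary assay. This is largely right. Blinded reading protects the measurement, however, and not whether a Day 7/14 sample exists; ITT retains the subject without supplying the missing value.

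A reader might go further and infer that eligibility itself is decided at surgery by someone who already knows the arm, for example through the criterion "The patient is not a candidate for a native fistula". The documents do not support that. Review of the criteria is pre-operative and precedes enrollment, and no readable criterion is described as something only vessel exposure can settle. Some exclusion criteria are redacted, so one can be neither assumed nor ruled out.

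Redaction also matters for timing. Most of Protocol 10.4 and SAP 2.5 is hidden, and SAP 4.1 breaks off where it would define enrollment. A rule restricting when the envelope is opened may sit there, and its absence from the readable text is not an error. But 5.5 is readable and expressly permits earlier opening, so a stricter rule elsewhere would have to be reconciled with it.

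Finally, a rule that opening must always follow vessel exposure would be too rigid: Protocol 1.2.8 describes an over-the-wire technique as well as open surgery, and the rule has not been shown to suit both.

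**Conclusion.** The point stands in a limited form. The readable text permits opening before surgery, leaves surgeon and subject unblinded, and discontinues randomized subjects who cannot complete the procedure. Decisions to stop, withdraw or switch can therefore be made with the arm known, and there is a device-specific reason why they might be more frequent in the test arm. That they would actually differ is a possibility, not something the documents show.

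The consequence is missing Day 7/14 results and cross-over, possibly unequal by arm. It is not selective entry into ITT, and a subject who switches graft is not misallocated under ITT. The size is unknown: each arm contributes a width equal to its own loss fraction. The 6-point illustration rests on assumed rates of 5% and 1% and holds only if every case is a dropout. No readable margin exists to judge it against. The mismatch between 5.5 and 9.4 is real but minor, covering about 2 days at most. The change is worth making because it is cheap, not because serious bias has been shown.

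**What to change.** In Protocol 5.5, remove the option of opening the envelope ahead of the procedure. Suggested text:

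> *The envelope is opened in the course of the index procedure, as late as the implantation technique allows and before any step specific to one arm, once the Investigator has recorded that the eligibility criteria still hold and that either a test or a control graft could be placed. Subjects who fail this check before opening are screen failures under section 5.4.*

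Then:

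- Record the time of opening on the Procedure CRF, and the reason for any non-implantation or switch of graft. Report both by arm.
- Reconcile 5.5 with 9.4 and the table in 5.2, so that the start of adverse-event reporting has one meaning.
- Reconcile it with any redacted text in Protocol 10.4, SAP 2.5 and SAP 4.1.
- If the redacted text does not already do so, state how ITT subjects without a Day 7/14 result are handled.

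The cost is protocol wording and a few CRF entries. Opening during the procedure is already allowed, so no new procedure is introduced. There are two small downsides: both graft types must be on hand in the operating room, and the check that either graft could be placed becomes an explicit condition, so some screen failures will be declared during the operation. Later opening should reduce arm-aware loss and switching but cannot be assumed to remove them.

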5.6 Procedure

CONFIDENTIAL INFORMATION

[REDACTED] Protocol Template

Revision#: 1

Doc Type: GC

Routine surgical practice for implantation of the vascular graft as an upper arm arteriovenous access for hemodialysis per the Investigator's standard of practice should be used. The test device, GORE® Hybrid Vascular Graft, is available in eight configurations listed in Section 1.2.5. The GHVG will be provided at standard cost.

5.6.1 Test Device Training Requirements

If the study Site has not used the GHVG, the study Site must complete device training prior to Subject enrollment.

5.6.2 Implantation Technique

The Investigator is expected to follow the Instructions for Use (IFU) for the test device or the control device, as determined by randomization.

5.6.3 Additional Implant Considerations

When implanting the GORE® Hybrid Vascular Graft or control device, the following considerations are recommended:

- The correct graft length for each procedure should be carefully determined according to the Investigator's standard practice.
- Any unused portions of the vascular graft must be destroyed according to institutional standards.
- Create a tight subcutaneous tissue tunnel.
- Avoid the use of traumatic clamps on vessels or vascular graft.
- If possible, avoid the use of systemic heparin during the index procedure.

The study procedure is considered to be a success once a thrill and / or bruit is noted through the implanted vascular access graft. The total procedural time, defined as the time from the first incision to the completion of closing of the last incision, will be recorded on the Procedure CRF.

[REDACTED]

[REDACTED]

[REDACTED]

CONFIDENTIAL INFORMATION

Protocol Template

Revision#: 1

Doc Type: GC

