Heparin-Induced Thrombocytopenia (HIT) is a potentially life threatening adverse reaction to heparin. Two forms of HIT have been described, HIT type I and HIT type II. The latter, HIT type II, is an immune-mediated reaction and is the more commonly discussed and more clinically significant version of HIT. The focus of this study is HIT type II and will hereafter be referred to simply as HIT. HIT is caused by heparin-dependent platelet-activating IgG antibodies that are formed in relation to an immunizing exposure to heparin, either unfractionated heparin (UFH) or low molecular weight heparin (LMWH). These antibodies recognize complexes of platelet factor 4 bound to heparin (PF4/H).⁶ In a subset of these patients, these antibodies activate. These antibodies are clinically significant causing activation and aggregation of platelets resulting in a falling platelet count. In some patients this can lead to thrombotic complications. Among patients receiving systemic heparin, the reported incidence of HIT is between 0.1% to 5.0% depending on the patient population and heparin type. HIT occurs more frequently in surgical patients and with unfractionated heparin (UFH) than with low molecular weight heparin (LMWH). Patients sensitive to heparin may frequently develop HIT antibodies, however, thrombocytopenia and thrombosis are relatively uncommon consequences.⁶

The GORE® Hybrid Vascular Graft is contraindicated for use in patients with known hypersensitivity to heparin including those patients who have had a known incident of HIT.

[REDACTED]

The risk of HIT for patients receiving systemic anticoagulant doses of heparin is low. Patients who receive the GORE® Hybrid Vascular Graft (GHVG) typically also receive systemic heparin both peri- and post-operatively and are therefore exposed to this low risk, independent of the implantation of a vascular graft [REDACTED]. An analysis of the [REDACTED] and [REDACTED] suggests that there is minimal risk that the covalently bonded heparin in the [REDACTED] causes or contributes to the condition of HIT.⁵

[REDACTED]

The clinical features of HIT include thrombocytopenia that bears a temporal relationship to the preceding immunizing exposure to heparin, thrombosis (venous or arterial), disseminated intravascular coagulation (DIC), post-UFH bolus anaphylactic reactions, limb gangrene, necrotizing skin lesions at heparin injection sites, among others.⁷

CONFIDENTIAL INFORMATION

Protocol Template

Revision#: 1

Doc Type: GC

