The key pathologic criterion for HIT is the presence of "HIT antibodies" as assessed by an in vitro SRA. The presence of HIT antibodies can be objectively determined with the SRA in concert with two enzyme immunoassays (EIAs), an IgG-specific EIA and a poly-specific EIA that detects antibodies of the Immunoglobulin G (IgG), Immunoglobulin A (IgA), and / or Immunoglobulin M (IgM) classes. A positive SRA has been shown to correlate strongly with the development of thrombocytopenia.⁸ An unusual feature of "HIT antibodies" is their remarkable transience: typically, among patients with well-documented HIT, antibodies become undetectable after 50 to 85 days (depending on the assay performed).⁹

Patients who receive the GORE® Hybrid Vascular Graft, or any other synthetic vascular graft, are typically given systemic heparin peri-operatively or post-operatively and / or in the dialysis unit during hemodialysis sessions. Therefore, these patients are exposed to the established low risk of HIT, independent of the [REDACTED]

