1.1. Study Rationale

The GORE® Hybrid Vascular Graft has been cleared by the U.S. Food and Drug Administration (FDA) in March 2010 for use in dialysis access patients, patients who require replacement or bypass of diseased vessels, trauma patients who need a vascular graft, and other vascular procedures.

Gore then submitted an application for CE-mark approval for the GORE® Hybrid Vascular Graft in 2012. The CE-mark was granted July 2012.

[REDACTED] Gore will conduct a controlled clinical study. Gore believes that a randomized, two-arm study to evaluate the prevalence and persistence of anti-PF4/heparin antibodies in GORE® Hybrid Vascular Graft patients versus a control arm (non-heparin bonded synthetic grafts) is the appropriate approach. By performing this type of controlled serology study, results of the study could potentially demonstrate there is no added risk of developing HIT antibodies through the use of a device [REDACTED]. In addition, the study could demonstrate that a device [REDACTED] does not influence the persistence of anti-PF4/H antibodies.

Background of HIT in Hemodialysis Patients:

The GORE® Hybrid Vascular Graft is used primarily for ESRD patients requiring hemodialysis through a synthetic graft. This study is to demonstrate that there is no added risk of developing HIT antibodies through the use of a device [REDACTED] (specifically the GHVG). The study will be conducted on a hemodialysis patient population in need of an upper arm synthetic arteriovenous (AV) access graft.

CONFIDENTIAL INFORMATION

[REDACTED] Protocol Template

Revision#: 1

Doc Type: GC

[REDACTED]

[REDACTED]

Background on HIT Assays:

Two general types of laboratory assays are used to confirm the presence of heparin-dependent IgG antibodies ("HIT" antibodies). Activation assays, such as the SRA, detect the antibodies based on their ability to activate platelets in a heparin-dependent fashion. Antigen assays, such as EIAs, detect the binding of antibodies to immobilized platelet factor 4-heparin complexes. The EIAs can be poly-specific (recognizing IgG, IgA and IgM immunoglobulin classes) or specific to detecting the IgG class alone. The antibodies associated with clinical HIT have been reported to be of the IgG class alone.

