7.1. Analysis Tables

- Subject Demographics [REDACTED]

CONFIDENTIAL INFORMATION

[REDACTED] Statistical Analysis Plan Template

Revision#: 1

Doc Type: GC

Page 12 of 14

- Subject Physical Exam [REDACTED]
- Subject Lab Results [REDACTED]
- Subject Medical History [REDACTED]
[REDACTED]
- Anticoagulant and/or antiplatelet therapies within the past 6 months [REDACTED]
[REDACTED]
- Summary of Enrollment by Site [REDACTED]
- Summary of Vascular Access History [REDACTED]
[REDACTED]
- Summary of Device Use [REDACTED]
[REDACTED]
- Summary of Procedural Assessments [REDACTED]
[REDACTED]
- Subject Status/Reason for Withdrawal [REDACTED]
[REDACTED]
[REDACTED]
- Summary of positive poly-specific enzyme immunoassay (EIA) [REDACTED]
- Summary of Anti-PF4/H antibody seroconversion
- Summary of Anti-PF4/H antibody seroreversion
- Summary of positive IgG-specific EIA at Day 7 and / or Day 14
- Summary of positive full serotonin release assay (SRA) panel
- Summary of platelet count at Pre-procedure, Day 7, 14, 30, and 90
[REDACTED]
[REDACTED]
[REDACTED]
[REDACTED]
- Summary of All Adverse Events by MedDRA SOC, PT

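### Does discretionary, unblinded systemic heparin at surgery require a new by-arm exposure table through Day 14?

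*Protocol*

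**What the plan says.** The Protocol's Introduction ties the antibodies to prior exposure to unfractionated or low molecular weight heparin. It adds that recipients of any synthetic graft "are typically given systemic heparin peri-operatively or post-operatively and / or in the dialysis unit during hemodialysis sessions". Section 1.1 states the aim: "This study is to demonstrate that there is no added risk of developing HIT antibodies through the use of a device".

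On practice at surgery, Section 5.6.3 introduces its list with "the following considerations are recommended", for test and control grafts alike, and the last item is "If possible, avoid the use of systemic heparin during the index procedure". Section 5.5 says the randomization envelope "is opened before or during the Index Procedure", and Section 10.5 says "The Subjects, as well as treating physicians, will be aware of the type of implanted graft". Only the core laboratory is blinded. The primary endpoint is a positive poly-specific immunoassay at Day 7 and/or Day 14 (Section 3.3.1).

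In the SAP, Section 7.1 lists a table titled "Anticoagulant and/or antiplatelet therapies within the past 6 months" and a summary of procedural assessments, each followed by redacted text. The opening of SAP Section 7 says the listed outputs are a minimum and are produced for each arm separately as well as combined.

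**The concern.** Heparin at the index procedure is given after randomization, by someone who may already know the arm. Randomization does not protect that exposure. SAP Section 5.5 attributes differences between arms to chance, but only for baseline characteristics.

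If surgeons gave less systemic heparin with the heparin-bonded graft, the control arm would carry more of the competing cause and a real device excess could be hidden. If they gave more, an excess could appear that the graft did not cause. In a study that hopes to find no difference, the first direction is the uncomfortable one. The visible anticoagulant table looks back six months and sits among the baseline tables, so it does not visibly cover the period from surgery to Day 14. A reader of the results might have no means of judging whether the arms were comparable on this point.

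**Working it through.** **Is the exposure shown to be unrecorded?** Set side by side, the sections do not show that.

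- Protocol 5.6.3 mentions the Procedure CRF (for procedural time) and is then followed by three redacted blocks. Protocol 5.7 also has redacted text.
- The Day 7 and Day 14 entries in Protocol 3.2 are unredacted and name only samples, adverse events and revisions. They are not complete lists, however: the Schedule of Events (5.2) also requires a physical exam and a thrill/bruit check at both visits.
- The SAP tabulates anticoagulant and antiplatelet therapy, yet neither the history text in Protocol Section 5 nor the schedule visibly names medication as a data item. Medication data are thus planned without visible protocol text, and silence is weak evidence of non-collection.
- The redacted procedural-assessments table in SAP 7.1 is the likeliest home for intra-operative heparin, and SAP Section 7 would already show it by arm.

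**How large would an imbalance need to be?** The plan has no figure to reproduce, because the hypothesis and sample size text is redacted. All inputs below are assumptions.

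Gap in heparin use (points) that fully hides a device excess = 100 × excess / heparin effect:

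| Device excess | Heparin adds 5 points | adds 10 | adds 15 |
|---|---|---|---|
| 2 points | 2/5 → 40 | 2/10 → 20 | 2/15 → 13.3 |
| 5 points | 5/5 → 100 | 5/10 → 50 | 5/15 → 33.3 |

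The same relation run forwards: distortion = (use in test − use in control) × (risk with heparin − risk without), taking 10% positivity without heparin.

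| Use, test v control | Risk with heparin 15% | 20% | 30% |
|---|---|---|---|
| 50% v 50% | 0 | 0 | 0 |
| 50% v 70% | −1 | −2 | −4 |
| 40% v 80% | −2 | −4 | −8 |
| 20% v 90% | −3.5 | −7 | −14 |

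For scale, the standard error of the antibody difference at 100 per arm is √(2 × p × (1 − p)/100). That is 4.2 points at p = 10%, 5.7 at 20% and 6.5 at 30%. Distortion of 1 to 2 points is well inside sampling error; the bottom row would not be.

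**What could a by-arm table resolve?** The 95% half-width for the gap in use is 1.96 × √(2 × p × (1 − p)/n).

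- At 50% use, the widest case: 1.96 × √(2 × 0.25/100) = 13.9 points at 100 per arm, and 1.96 × √(2 × 0.25/50) = 19.6 at 50 per arm.
- At 20% or 80% use: 1.96 × √(2 × 0.16/100) = 11.1 at 100 per arm, and 1.96 × √(2 × 0.16/50) = 15.7 at 50 per arm.

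With half-widths of 11 to 20 points, gaps of 33 to 50 points would be visible. The 13- to 20-point gaps that could hide a 2-point excess could not be relied on to show up or be excluded.

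**The case for a change.** The strongest case for a change is that the mechanism rests on visible text at every step and that post-allocation heparin is outside randomization's protection. The Day 7 and Day 14 visit entries carry no redaction, and the one redacted row of the schedule is not marked at either visit, so the apparent gap is clearest for post-operative and dialysis heparin. One descriptive table would cost little if the data exist. If they do not, exposure not recorded at the time may be hard to recover later. A table showing similar use would also help the sponsor's own conclusion.

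The mechanism stands, and so does the point that a large imbalance would be worth seeing. The rest is weaker. Dialysis heparin is the costliest item to retrieve and the least exposed to this bias: no section gives the surgeon that decision, and its baseline level should be balanced by randomization. No section predicts a gap at surgery, where both arms receive the same advice. The assumed heparin effects compare exposure with none, whereas these patients are typically exposed at some point anyway; what one intra-operative exposure adds is not given. Because the exposure follows randomization, covariate adjustment would not be a simple remedy either, so the table could only describe.

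**Conclusion.** No change to the plan is needed. Systemic heparin is a real competing cause and its use at surgery is open to arm-dependent choice, but the documents do not show that it goes unrecorded: the relevant procedure, follow-up and table text is partly redacted, and redacted text does not count as missing. If procedural heparin is captured, the SAP's existing by-arm, minimum-set rule lets the analysts include it in the procedural summary without amendment. Anyone with the unredacted forms can check capture as a low-priority query.

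The size of the issue rests wholly on assumed inputs: heparin effects of 5 to 15 points, device excesses of 2 to 5 points, and 50 to 100 subjects per arm. On those figures modest imbalances distort the comparison by less than its sampling error. The imbalances that would matter most are very large ones that nothing in the documents leads one to expect. An added table would leave the intent-to-treat result unchanged and could not settle whether a smaller gap had mattered.
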